8.3. Patient Withdrawal Criteria

Patients may be discontinued from the trial for the following reasons:

- Death
 - An autopsy and/or post-mortem tissue/organ collection will be requested for any patient who expires following participation (see Post-Mortem Tissue and Organ Collection Plan in [Appendix 2](#))
- Failure to comply with protocol-required visits or trial procedures for 3 or more consecutive visits that are not rescheduled, unless due to hospitalization
- Parent(s)/legal guardian(s) withdraws consent
- Investigator discretion

End-of-Trial procedures should be completed within 14 days for any patient who prematurely discontinues the trial for any reason, as indicated in [Appendix 1](#). Patients who terminate the study early for reasons other than death will be offered enrollment in a long-term follow-up study.

In instances in which a patient withdraws from the study prior to the last scheduled visit, the investigator should differentiate between factors that are related to a catastrophe (such as the inability to travel, local ordinances or other restrictions, etc.) versus withdrawal of consent.

9. TREATMENT OF PATIENTS

It is the responsibility of the Investigator to ensure the safe storage and administration of gene replacement therapy.

9.1. Description of Trial Product

AVXS-101 is a non-replicating recombinant AAV9 containing the *SMN* gene under the control of the cytomegalovirus (CMV) enhancer/ CB. One of the 2 AAV inverted terminal repeats (ITRs) has been modified to promote intramolecular annealing of the transgene, thus forming a double stranded transgene ready for transcription.

Table 2: Investigational Product

	Investigational Product
Product Name	AVXS-101
Unit Dose	1.1×10^{14} vg/kg; Equivalent to the dose received by the Cohort 2 in the Phase 1 study (AVXS-101-CL-101) as determined by direct product testing with improved analytical methods.
Route of Administration	Intravenous infusion
Physical Description	AVXS-101 is a clear, colorless to faint white solution.

9.2. Prior and Concomitant Medications

Prior and concomitant medications will be captured in the electronic Case Report Form (eCRF) from 2 weeks prior to administration of gene replacement therapy through the last trial visit.

9.2.1. Prophylactic Administration of Prednisolone

An antigen specific T-cell response to the AAV vector was observed in the completed Phase 1 clinical trial (AVXS-101-CL-101) investigating AVXS-101 treatment via IV infusion [data on file]. This is an expected response between 2 to 4 weeks following gene replacement therapy. One possible consequence to such antigen specific T-cell response is clearance of the transduced cells and loss of transgene expression.

In an attempt to dampen the host immune response to the AAV based therapy, all patients will receive prophylactic prednisolone at approximately 2 mg/kg/day (or an equivalent dose of another glucocorticoid if prednisolone is unavailable or in the opinion of the investigator prednisolone is not tolerated [41]) on Day -1, Day 1, and Day 2, and then 1 mg/kg/day starting on Day 3 and until at least 30 days post-AVXS-101 infusion. After 30 days post-AVXS-101 infusion, the dose of prednisolone can be tapered for patients whose GGT, ALT, and AST values are below the threshold of $2 \times$ ULN. To summarize, the overall course of prednisolone should follow the following treatment guideline:

- Day -1, Day 1, and Day 2: 2 mg/kg/day
- Day 3 until at least 30 days post AVXS-101 infusion: 1 mg/kg/day

- Weeks 5 and 6 post-AVXS-101 infusion: 0.5 mg/kg/day
- Weeks 7 and 8 post-AVXS-101 infusion: 0.25 mg/kg/day
- Week 9 post-AVXS-101 infusion: prednisolone discontinued

Liver function testing should guide each step of the taper, and liver function tests should be checked prior to prednisolone discontinuation. If the GGT, AST, or ALT values are $\geq 2 \times$ ULN, then the present dose of prednisolone will be adjusted as needed until the GGT, AST, and ALT values decrease below threshold, at which point the taper may continue. Liver function tests should also be checked approximately 2 weeks after the taper has concluded and prednisolone has been discontinued to evaluate for rebound elevation of GGT, AST, or ALT levels. Variance from these recommendations will be at the discretion of the Investigator based on potential safety issues for each patient. If another glucocorticoid is used in place of prednisolone by the Investigator, similar considerations should be taken into account after 30 days and tapered as appropriate and at the discretion of the Investigator.

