In an attempt to dampen the host immune response to the adeno-associated virus (AAV) derived therapy, all patients will receive prophylactic prednisolone at approximately 2 mg/kg/day (or an equivalent dose of another glucocorticoid if prednisolone is unavailable or in the opinion of the investigator prednisolone is not tolerated [39]) on Day -1, Day 1, and Day 2, and then 1 mg/kg/day starting on Day 3 and until at least 30 days post-AVXS-101 infusion. After 30 days post-AVXS-101 infusion, the dose of prednisolone can be tapered for patients whose gamma glutamyl transferase (GGT), alanine aminotransferase (ALT) values, and aspartate aminotransferase (AST) values are below

the threshold of $2 \times$ Upper Limit Normal (ULN) in accordance with the following treatment guideline: taper from 1 mg/kg/Day to 0.5 mg/kg/Day during Weeks 5 and 6 post-AVXS-101 infusion, then taper to 0.25 mg/kg/Day during Weeks 7 and 8, and then discontinue prednisolone at Week 9. If the AST or ALT values are $> 2 \times$ ULN, the dose of prednisolone will be maintained until the AST and ALT values decrease below threshold. Variance from these recommendations will be at the discretion of the Investigator based on potential safety issues for each patient. If another glucocorticoid is used in place of prednisolone by the Investigator, similar considerations should be taken into account after 30 days and tapered as appropriate and at the discretion of the Investigator.

Efficacy will be assessed by achievement of the key developmental milestone of sitting without support for at least 10 seconds based on World Health Organization [WHO] Child Growth Standards at any point up to and including the 18 months of age trial visit, and survival at 14 months of age.

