Importantly, in instances in which the final scheduled study visit is not possible to be conducted at the study site or the scheduling of the final scheduled study visit is at risk of delay due to travel restrictions or other circumstances, the final scheduled study visit should be performed all or in part remotely within the protocol-defined visit window. Critical data that pertain to the co-primary and co-secondary endpoints and other information such as adverse events, concomitant medications, use of feeding or ventilatory support, or other safety data that may be obtained remotely should be collected as part of the final study visit and within the protocol-defined visit window.

Procedures such as laboratory and other safety assessments that cannot be performed or obtained as part of a remote visit may be performed separately and preferably within the protocol-defined visit window.

Figure 4: Trial Design

Note: After the End of Trial visit at 18 months of age or at the time of early discontinuation patients will be invited to participate in a long term follow up study conducted under a separate protocol.

^a All post-treatment visits will be relative to the date on which gene replacement therapy ("dose") is administered until the patient is 14 months of age, after which all visits will be relative to the patient's date of birth. Note: Depending on the patient's age at dosing, the duration of participation at the end-of-trial visit can vary from approximately 12 months (baby dosed at approximately 6 months of age) to approximately 18 months (baby dosed near birth "0 months of age").

In an attempt to dampen the host immune response to the AAV derived therapy, all patients will receive prophylactic prednisolone at approximately 2 mg/kg/day (or an equivalent dose of another glucocorticoid if prednisolone is unavailable or if, in the opinion of the investigator, prednisolone is not tolerated [41]) on Day -1, Day 1, and Day 2, and then 1 mg/kg/day starting on Day 3 and until at least 30 days post-AVXS-101 infusion. After 30 days post-AVXS-101 infusion, the dose of prednisolone can be tapered for patients whose gamma glutamyl transferase (GGT), ALT values, and AST values are below the threshold of $2 \times$ ULN in accordance with the

following treatment guideline: taper from 1 mg/kg/day to 0.5 mg/kg/day during Weeks 5 and 6 post-AVXS-101 infusion, then taper to 0.25 mg/kg/day during Weeks 7 and 8, and then discontinue prednisolone at Week 9.

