Trial Period	Screening	Gene Replacement Therapy (In-patient)					Follow-up (Outpatient)										Notes	
		-1	1	2	3	7	14	21	30	44	60 (or Month 2)	72	90 (or Month 3)	Month 4,5,7,8,10,11,13	Month 6,9,12	End of Trial (18 months of age or ET)		
Nominal Study Day (Visit Relative To Dose)	-30 to -2																	Depending on the patient's age at dosing, the duration of participation can vary from approximately 12 months (baby dosed at approximately 6 months of age) to approximately 18 months (baby dosed near birth, "0 months of age").
Visit According To Months of Age														14,16,17	15			
Window	(No Window)					± 2 days					± 7 days (Except +0-14 days at 14 Months of Age)					+0-14 days		
AAV9 Ab Screen in Biological Mother	X																	See Section 12.1.10.7 .
Blood for Diagnostic Confirmation Testing	X																	See Section 12.1.10.8 .
Saliva, Urine, and Stool Samples (for viral shedding)	X			(X)	(X)	X	X	X	X									See Section 12.1.10.9 . (X): Collected within 24 and 48 hours post dose.
Prophylactic Prednisolone		X	X	X	X	X	X	X	X	(X)	(X)							See Section 9.2.1 . (X): After 30 days, prednisolone (or equivalent glucocorticoid) can be tapered for patients whose ALT values, and AST values are below the threshold.
Adverse Events	X	X	X	X	X	X	X	X	X	X	X	X	X	X	X	X	X	See Section 13 .
Prior and Concomitant Medications	Collected from 2 weeks before gene replacement therapy until End of Trial visit																	

Ab = antibody; ALT = alanine aminotransferase; AST = aspartate aminotransferase; BSIDv03 = Bayley Scales of Infant and Toddler Development version 3; CBC = complete blood count; CHOP INTEND = Children's Hospital of Philadelphia Infant Test of Neuromuscular Disorders; CK-MB = Creatinine kinase-muscle/brain; ECG = electrocardiogram; ELISA = enzyme-linked immunosorbent assay; ET = early termination; GGT = gamma glutamyl transferase; IRB = Institutional Review Board; LFT = liver function tests; WHO = World Health Organization

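### The synopsis and Protocol Section 9.2.1 give conflicting rules for holding the prednisolone taper once it has begun; the Schedule of Assessments note and SAP 7.4.1 diverge from both on the tests

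*Protocol*

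**What the plan says.** All the text compared here is current; none comes from an amendment log.

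**Starting the taper.** The protocol synopsis says that after 30 days "the dose of prednisolone can be tapered for patients whose gamma glutamyl transferase (GGT), alanine aminotransferase (ALT) values, and aspartate aminotransferase (AST) values" are below 2 x ULN. Section 7.1 has the same three tests ("gamma glutamyl transferase (GGT), ALT values, and AST values are below the threshold of" 2 x ULN), and so does Section 9.2.1 ("the dose of prednisolone can be tapered for patients whose GGT, ALT, and AST values are below the threshold of" 2 x ULN).

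**Holding the taper.** The synopsis rule opens "If the AST or ALT values are" above 2 x ULN, and then "the dose of prednisolone will be maintained until the AST and ALT values decrease below threshold". The Section 9.2.1 rule opens "If the GGT, AST, or ALT values are" at or above 2 x ULN, and "then the present dose of prednisolone will be adjusted as needed until the GGT, AST, and ALT values decrease below threshold", after which tapering may resume. Section 7.1 has no hold rule.

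**Other places.** The prednisolone note in the Appendix 1 Schedule of Assessments, repeated in SAP Table 1, points to Section 9.2.1 and says the drug "can be tapered for patients whose ALT values, and AST values are below the threshold". It does not mention GGT and gives no number. SAP 7.4.1 describes tapering for patients with ALT and AST at or below 2 x ULN and a T-cell response under 100 SFC per million PBMC, again without GGT.

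The synopsis and Section 9.2.1 both let the investigator vary from the recommendations for safety reasons in the individual patient.

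**The concern.** Two investigators who both follow the protocol, and neither of whom uses the discretion clause, can manage the same liver result differently depending on which page they read.

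The instruction is safety-relevant. Protocol Section 5.5 names transient liver enzyme elevations, resolved after prednisolone, as the safety events that appear to be associated with the product. Section 13.1.3 lists hepatotoxicity as an adverse event of special interest. Section 9.2.1 says liver testing should guide each taper step.

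There is also a reporting side. SAP 7.4.1 plans to summarise each patient's days on prednisolone and cumulative dose. If sites applied different hold rules, part of the variation in exposure reflects which text was followed. The graded and ULN-multiple liver tables in SAP 10.4.3 do not include GGT, so they would not explain a taper prolonged because of GGT.

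**Working it through.** No figure in the plan needs reproducing. The check sets the texts side by side and then runs cases through them.

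| Source | Tests to start taper | Tests that hold it | Hold boundary | Stated action | Released when |
|---|---|---|---|---|---|
| Protocol synopsis | GGT, ALT, AST below 2 x ULN | AST or ALT | > 2 x ULN | dose maintained | AST and ALT below threshold |
| Protocol 7.1 | GGT, ALT, AST below 2 x ULN | none given | – | – | – |
| Protocol 9.2.1 | GGT, ALT, AST below 2 x ULN | GGT, AST or ALT | >= 2 x ULN | dose adjusted as needed | GGT, AST and ALT below threshold |
| Appendix 1 note (and SAP Table 1) | ALT, AST below an unstated threshold; refers to 9.2.1 | none given | – | – | – |
| SAP 7.4.1 | ALT, AST <= 2 x ULN, plus T-cell criterion | none given | – | – | – |

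**Case 1: during the taper, AST or ALT above 2 x ULN.** Both hold rules are triggered. The synopsis maintains the dose; Section 9.2.1 adjusts it as needed. If GGT is also raised, release differs too: the synopsis waits for AST and ALT, Section 9.2.1 for all three. This is the broadest conflict, because it needs neither an isolated GGT rise nor a boundary value.

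**Case 2: during the taper, GGT above 2 x ULN with AST and ALT below it.** Section 9.2.1 is triggered; the synopsis hold rule is not.

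**Case 3: during the taper, AST or ALT exactly 2 x ULN, GGT below.** Section 9.2.1 is triggered; the synopsis is not, although the value is not below threshold. The enzyme part of SAP 7.4.1 is met.

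**Case 4: at about Day 30, GGT raised alone.** The synopsis, 7.1 and 9.2.1 all withhold the start of the taper. The Appendix 1 note, read without its cross-reference, would allow it. So would SAP 7.4.1 if its T-cell criterion is met.

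**Would the results be seen?** Yes. The Schedule of Assessments has chemistry at Days 30 and 60 and liver tests including GGT at Days 44 and 72. If Week 1 is Days 1 to 7, Week 7 starts on Day 6 x 7 + 1 = 43, so the Day 44 sample falls at the second taper step.

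**Could sites apply the SAP's T-cell criterion?** The protocol's Schedule of Assessments lists only ELISA under immunological testing, so the current schedule contains no T-cell sample on which to base it.

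**Timing.** The synopsis estimates last completion in Q3 2020, so 30 September 2020 at the latest. Follow-up is at least about 12 months (Figure 4 note), which puts last dosing at about 30 September 2019. Adding 9 weeks (63 days) for the scheduled taper gives about 2 December 2019. This protocol version is dated 25 June 2020.

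**The case against.** Several points on the other side are sound.

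- **The start rule is consistent.** A reader might infer that any infant with raised GGT is handled differently throughout. The documents do not support that: the synopsis, 7.1 and 9.2.1 all require GGT below 2 x ULN before tapering starts. The GGT conflict between the synopsis and 9.2.1 arises once the taper has begun.
- **There are not three complete rival rules.** The Appendix 1 note has no number, no hold rule and no action, and it sends the reader to Section 9.2.1. Its omission of GGT is a drafting gap. Boundary and action conflict between two texts only.
- **Adjusting as needed can include no change.** This narrows Case 1 but does not close it, because one text fixes the dose and the other leaves it open.
- **Discretion is written in.** It permits departure from a recommendation. It does not say which of two is the recommendation.
- **The data can still be described.** A reader might infer that hepatic results or steroid exposure become uninterpretable. That goes too far. Exposure is derived from the prednisolone log, chemistry at all visits includes GGT, AST and ALT, GGT is among the SAP 10.4.2 variables, and hepatotoxicity is collected whatever its grade. What is lost is the reason for some of the variation between sites.
- **Most tapers were probably over by this version.** On the protocol's own estimates this stands, and it limits what an amendment could change. Earlier versions are not among the documents, so past handling is unknown.

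**Conclusion.** The point holds for the hold rule. The synopsis and Section 9.2.1 differ in the tests, the boundary, the action and the condition for release, and nothing in the protocol says which prevails. The Appendix 1 note and SAP 7.4.1 are secondary inconsistencies. SAP 7.4.1 is the furthest from the rest, but as an analysis document it bears on how the regimen is described rather than on how sites treat.

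The size in patients cannot be given: the documents report no frequency of AST, ALT or GGT elevation during the taper. In kind, Case 1 matters most, Case 2 next, and Case 3 is confined to a single exact value. The primary and secondary efficacy tests do not use the taper rule and are not directly affected.

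The conclusion rests on reading the synopsis and Section 9.2.1 as equally operative. The view that tapers were mostly complete rests on the protocol's estimated dates and an unprolonged taper. It is worth correcting as a safety instruction tied to an adverse event of special interest and to a planned exposure summary; it does not threaten the trial's main conclusions.

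**What to change.** Reconcile the synopsis, Section 9.2.1, the Appendix 1 note with its copy in SAP Table 1, and SAP 7.4.1, so that each gives the same list of tests, the same boundary and the same action. The choice among the existing texts belongs to the sponsor's clinical team; this review takes no position on it. SAP 7.4.1 must be included, or a conflict remains after the protocol is corrected.

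The cost is wording only: a protocol amendment or clarification letter, plus a SAP correction. If all tapers are already complete, state in the clinical study report which rule sites followed, next to the prednisolone exposure and hepatic results.

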9.2.2. Prohibited Medications

Concomitant use of any of the following medications is prohibited:

- Drugs for treatment of myopathy or neuropathy, or agents used to treat diabetes mellitus
- Therapy received with the intent to treat SMA (e.g., nusinersen, valproic acid); oral β -agonists must be discontinued at least 30 days prior to gene therapy dosing. Inhaled β -agonists may be used to treat respiratory complications of SMA provided such medications are dosed at clinically appropriate levels
- Any investigational medication other than AVXS-101 is prohibited during the trial
- Ongoing immunosuppressive therapy, plasmapheresis, immunomodulators such as adalimumab, or immunosuppressive therapy within 3 months prior to AVXS-101 dosing (e.g., corticosteroids, cyclosporine, tacrolimus, methotrexate, cyclophosphamide, IV immunoglobulin, rituximab)

Corticosteroid usage following completion of the prednisolone taper is permissible as part of routine clinical management. The use of corticosteroids in such circumstances should be documented appropriately as a concomitant medication, and the event precipitating its usage should be appropriately documented as an adverse event.

Should the use of corticosteroids (aside from inhaled corticosteroids for bronchospasm) be considered as part of care during the course of the prednisolone taper, this medical management should be discussed with the medical monitor.

9.2.3. Vaccinations

Where feasible, the vaccination schedule should be adjusted appropriately to accommodate the prednisolone use. When avoiding vaccination while on steroids represents an undue delay or interruption of a vaccination schedule, vaccination should continue at the discretion and judgement of the treating physician given 1) the importance of maintaining childhood

AveXis, Inc.

AVXS-101-CL-302

Investigational Product: AVXS-101

Protocol Version 7.0/Amendment 6/25 Jun 2020

vaccination in this population and 2) the published literature that indicates that vaccination while on steroid doses 1 mg/kg/day or below is safe and effective [43].

Vaccinations that include palivizumab (also known as Synagis[®]) prophylaxis to prevent respiratory syncytial virus infections are also recommended (31, 44).

9.3. Treatment Compliance

AVXS-101 will be administered as a one-time IV injection.

9.4. Randomization and Blinding

This is an open-label trial.

10. TRIAL PRODUCT MATERIALS AND MANAGEMENT

AVXS-101 is manufactured in accordance with current Good Manufacturing Practices (cGMP).

10.1. Trial Product

AVXS-101

10.2. Trial Product Dose and Dose Justification

Patients will receive a 1-time dose of AVXS-101 at 1.1×10^{14} vg/kg, equivalent to the dose received by Cohort 2 in the Phase 1 study via IV infusion administered in the completed Phase 1 clinical study (AVXS-101-CL-101).

Two doses were studied in the completed Phase 1 clinical study (AVXS-101-CL-101); the higher dose (dose received by the Cohort 2 patients) was chosen for the present study as preliminary data demonstrated both a dose response and significant clinical benefit thus identifying it as the proposed therapeutic dose. In the Phase 1 study, AVXS-101 demonstrated a dose response, with efficacy greater as observed by motor milestone achievement and CHOP INTEND scores at the higher dose (received by Cohort 2) than at the lower dose (received by Cohort 1). Direct testing of the actual lot of Investigational Medicinal Product (IMP) used in the AVXS-101-CL-101 study by an improved and more fully qualified analytical method has assigned a value of 1.1×10^{14} vg/kg to the actual dose received by Cohort 2 in this Phase 1 study. The same method has been used to establish an equivalent dose for the Phase 3 IMP. This vg/kg value has been further verified in an improved and more fully qualified SMN Δ 7 Mouse Biopotency assay to support a similar extension of mouse lifetime in direct comparative assessment between the Phase 1 and Phase 3 IMP.

10.3. Trial Product Packaging and Labeling

AVXS-101 kits will be labeled with a specific kit number and batch/lot number assigned at the cGMP facility. The content of the labeling is in accordance with the local regulatory specifications and requirements.

10.4. Trial Product Storage and Destruction

AVXS-101 kits will be stored in a locked, limited access room under the responsibility of the Investigator or other authorized persons (e.g., pharmacists) in accordance with local regulations, policies, and procedures. Control of storage conditions, especially control of temperature (e.g., refrigerated/freezer storage) and information on in-use stability and instructions for handling prepared AVXS-101 should be managed in accordance with the Pharmacy Manual.

The vessel used for delivery of the vector should be resealed in the procedure room and processed for destruction in accordance with the Pharmacy Manual and applicable biohazardous waste guidelines for disposal.

